10.1 Inclusion Criteria

The school and child inclusion criteria are shown as follows:

School (cluster) inclusion criteria:

- Run by the Local Education Authority/borough, providing mainstream education.
- In London or the home counties
- With an intake at Year 4 (children aged 8-9 years) and Year 5 (children aged 9-10 years)

Student inclusion criteria:

- All children in Year 4 (aged 8-9 years)

10.2 Exclusion Criteria

School (Cluster) exclusion criteria:

- Private or specialist schools.

Student exclusion criteria:

- None

11. Trial Intervention

11.1 Interventions

11.1.1 Waitlist control Schools

The usual school curriculum will be delivered to all children, irrespective of receipt of CUES-Ed. The usual school curriculum is nationally set, with limited scope for variation by school. We will record what is delivered in the usual curriculum, but will not interfere with usual delivery. In particular, as CUES-Ed will not comprise

additional hours of teaching, we will record any difference arising in the routine curriculum delivered in intervention and waitlist control schools.

11.1.2 Intervention Schools

CUES-Ed comprises 7 modules, delivered over 16 weeks, in sessions of 20 minutes, three times/week. The programme consists of digital interactive sessions. Teachers need only to run the session: content and interactivities are part of the package. The package relies on appealing branding, and engaging characters. This is crucial when working with children, and has been a key feature noted positively in feedback to date. Children in the intervention arm will receive CUES-Ed straight away. Children in the waitlist control arm will receive CUES-Ed later in the term or in the following academic year.

11.2 Teachers

The intervention is designed to be delivered by teachers with minimal training. Instructions for the use of the package will be delivered during a thirty minute video compiled by the research team. This will be given to teachers after randomisation.

11.3 Adherence

Teacher adherence to the programme will be assessed by a classroom observation, using a checklist, which will be standardised as part of the pilot study. The intervention material itself is pre-prepared. Teachers will be rated on their presentation and discussion of the material. Sessions will be pseudorandomly selected in advance and blind to school and teacher, to ensure beginning, middle and end sessions are all sampled.

Child attendance will be measured according to the register for the school session; the teacher will routinely record any children sitting out that session, and teachers and heads agree as part of the school/teacher consent process to collect that information for the research team.

12. Outcomes

12.1 Primary outcome measures

For the feasibility outcomes the parameters are based upon the following progression criteria:

Criteria	Green (Go)	Amber (Proceed with changes)	Red (Not feasible to proceed)
Randomise schools	10	8	<8
Consent/Baseline data for children from parents	360/600=60%	240/600=40%	<240/600
Child assent	360/600=60%	240/600=40%	<240/600
Children providing baseline data	360/600=60%	240/600=40%	<240/600
Followed up	%80	70%	<70%
Adherence of teachers	%80	70%	<70%
Fidelity of intervention*	%80	70%	<70%

* Fidelity is determined by whether CUES-Ed schools get CUES-Ed and waitlist control schools do not get CUES-Ed between 0-16 weeks

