7.1 Trial Objectives

Aims: We plan to test the feasibility of our trial procedures for a subsequent study evaluating the effectiveness of the CUES-Ed intervention, as an adjunct to the usual school curriculum, compared to the usual school curriculum alone, in reducing emotional and behavioural problems in vulnerable Year 4 schoolchildren in England, receiving the intervention as part of a whole class.

Feasibility will be judged as being able to: randomise schools; obtain parental consent for the use of data for research purposes; deliver the intervention adherently; ensure child attendance; complete child and teacher outcomes at scheduled times (0, 8 and 16 weeks), within a one month window for completion at each timepoint (i.e. between 6 and 10 weeks for the 8 week assessment and between 14 and 18 weeks for the 16 week assessment), with retention from baseline to follow-up. Secondary aims will be to estimate parameters for a sample size calculation for the subsequent larger trial, standardise our measures of adherence of teacher delivery, and validate our teacher-rated measure of classroom behaviour and child quiz.

The sample for the study will comprise consenting (n=360) children in ten schools.
Criteria for judging feasibility are as follows:

7.1.1 Randomising schools:

- Randomisation according to allocation without contamination for all ten schools

7.1.2 Parental and child consent:

- ≥ 60% of targeted parents (i.e. parents of children in participating classes) giving informed consent for data use (n=360, from 600)

7.1.3 Adherent delivery:

- Of the ten teachers delivering the intervention, at least eight achieving acceptable adherence ratings for an observed session

7.1.4 Outcome completion:

- ≥80% of children completing outcome measures and giving assent for these to be used for research (n=288, from 360).

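### One waitlist school receiving CUES-Ed fails the feasibility criterion in 7.1.1 but still rates Green for fidelity in 12.1

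*Protocol*

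**What the plan says.** Section 7.1 of the protocol introduces its list with "Criteria for judging feasibility are as follows". The first item, 7.1.1, is "Randomisation according to allocation without contamination for all ten schools". It allows no exceptions.

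Section 12.1 introduces its Green / Amber / Red table with "For the feasibility outcomes the parameters are based upon the following progression criteria". The row "Fidelity of intervention" carries one figure per colour: 80%, 70%, and below 70%. The footnote to that row reads "Fidelity is determined by whether CUES-Ed schools get CUES-Ed and waitlist control schools do not get CUES-Ed between 0-16 weeks". The row gives no denominator and no separate figure for either arm.

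The first row of the same table concerns randomising schools (Green 10, Amber 8, Red below 8). It does not mention contamination.

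**The concern.** Both sections set rules for judging feasibility, and both cover whether a waitlist school receives CUES-Ed during follow-up. Section 7.1.1 tolerates no such school. Section 12.1 gives Green at 80%, which tolerates at least one. The same result can therefore be a failed criterion in one section and a Go in the other, and the protocol does not rank the two.

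A second problem lies in how the row is built. If one percentage covers both arms, full delivery in the CUES-Ed schools offsets exposure in the waitlist schools. Non-delivery in the intervention arm and contamination of the control arm are different faults with different remedies, and a pooled figure cannot tell them apart.

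Fidelity is one of seven rows that decide whether the main trial goes ahead. The pilot is also meant to supply a between-group summary on Me and My Feelings (20.2) and parameters for sizing the full trial (12.2). Exposed control schools would blur that contrast, and readers of the table should be able to see that it happened.

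**Working it through.** **Inputs**

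- Schools: 10 (Protocol 7.1).
- Allocation: 1:1 by school (Protocol 8.1), so 10 / 2 = 5 per arm.
- Fidelity thresholds: Green 80%, Amber 70%, Red below 70% (Protocol 12.1).
- Contaminated schools tolerated by 7.1.1: 0.
- Unit: the school, as the 12.1 footnote is worded.

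The 80% is a chosen threshold, so there is no calculation of the plan's to reproduce. Counted over ten schools, 0.80 × 10 = 8, so Green tolerates two failures. Amber is 0.70 × 10 = 7, which tolerates three.

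**Formulas.** Let *a* be the number of CUES-Ed schools that do not deliver and *k* the number of waitlist schools that receive CUES-Ed.

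- Pooled fidelity = (10 − a − k) / 10
- Waitlist-arm fidelity = (5 − k) / 5
- Share of the control arm exposed = k / 5

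**Results with all CUES-Ed schools delivering (a = 0)**

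| k | 7.1.1 | 12.1, pooled | 12.1, waitlist arm alone | Control schools exposed |
|---|---|---|---|---|
| 0 | met | 10/10 = 100%, Green | 5/5 = 100%, Green | 0% |
| 1 | not met | 9/10 = 90%, Green | 4/5 = 80%, Green | 20% |
| 2 | not met | 8/10 = 80%, Green | 3/5 = 60%, Red | 40% |
| 3 | not met | 7/10 = 70%, Amber | 2/5 = 40%, Red | 60% |

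The row k = 1 carries the finding: 7.1.1 is not met, and 12.1 is Green under either way of counting schools. To match 7.1.1, the Green threshold would have to exceed 90% if pooled, or 80% if applied to the waitlist arm alone.

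**Offsetting.** A pooled score of exactly 80% arises from (a, k) = (0, 2), (1, 1) or (2, 0). These are two exposed control schools, one fault in each arm, and two intervention schools that did not deliver. The table would rate all three alike.

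**The case against.** The strongest reply is that 7.1.1 belongs with the first row of the 12.1 table. Its heading is about randomising schools, it requires all ten, and that row is Green at 10. On this reading fidelity is a further, graded measure. Two criteria of different strictness can coexist, and the stricter one decides. The protocol may have intended this, but it does not say so. The first row does not mention contamination, so one contaminated school would leave it at Green, and the fidelity row would be Green as well. Nobody reading the table alone would learn that 7.1.1 had failed.

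A second reply is that the denominator for fidelity can be left to the statistical analysis plan. That is fair as to pooling: pooling is inferred from a single percentage and a footnote that joins the arms, and a reader should not take two of five exposed schools as something the protocol states. Scored by arm, Green stops at one of five. The disagreement with 7.1.1 remains either way, because both thresholds are fixed in the protocol.

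A third reply is that a pilot may reasonably accept some contamination and that no hypothesis tests are run on the feasibility outcomes (20.1). Both are true. If some contamination is acceptable, 7.1.1 is the text to change.

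**Conclusion.** The point stands as a minor inconsistency in a decision rule. One contaminated waitlist school is a failure under 7.1.1 and Green under 12.1, at 90% pooled or 80% by arm. The pooled figure assumes that all five CUES-Ed schools deliver. Both figures assume five schools per arm, which follows from ten schools at 1:1. If the arms are pooled, Green extends to two of five waitlist schools (40%).

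A reader might infer more than the protocol supports:

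- **That contamination is likely, or that its cost to the main trial can be calculated.** Schools are recruited because they know the service (section 9), but that is not the same as delivering the digital package. The training video is given after randomisation (11.2), and section 13 assigns it to intervention-arm teachers. No contamination rate is given, nor any effect in exposed schools, so a diluted effect or an inflated sample size would rest on assumptions alone.
- **That contamination is the only place where 7.1 and 12.1 part.** Consent matches: 7.1.2 asks for 60% of parents "giving informed consent for data use", and 12.1 also has 60%. Adherence matches: "Of the ten teachers delivering the intervention, at least eight achieving acceptable adherence ratings for an observed session" is 8/10 = 80%. But 7.1.4 asks for 80% (288 of 360) "of children completing outcome measures and giving assent for these to be used for research", whereas 12.1 scores assent in its own row at 360/600 and follow-up in another at 80%.
- **That the footnote's week-16 limit leaves a gap before late assessments.** Section 13 already requires the waitlist outcomes to be completed without the programme.

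**What to change.** Split the fidelity row of 12.1 by arm, with the school as the unit in both parts.

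- **CUES-Ed arm:** schools that deliver CUES-Ed in the intervention period, keeping 80% / 70% / below 70%.
- **Waitlist arm:** Green when none of the five schools receives CUES-Ed before its own 16-week assessment, to match 7.1.1. The team sets the Amber and Red cut-offs.

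Add a sentence to 7.1.1 saying that its contamination clause is judged by the waitlist row. If the team is willing to accept some contamination, keep a tolerance in 12.1 and state the tolerated number of waitlist schools in 7.1.1, so that the two agree.

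The cost is one row made into two, a reworded footnote and one cross-reference. The only data needed are whether and when each waitlist school first used CUES-Ed. There are two consequences to accept. One contaminated waitlist school would no longer read Green. And with five schools per arm the percentage moves in steps of 20 points (4/5 = 80%, 3/5 = 60%), so no result in the CUES-Ed row can fall in the Amber band; the team may prefer to write that row as counts.

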12.2 Secondary outcome measures

Parameter estimation to determine sample size for a full trial will be based on outcomes on the proposed primary clinical outcome measure, M&MF (see 12.3).

Validation of the classroom based outcome measure (see 12.3) will be done through psychometric testing of collected data and comparison of teacher ratings to an observer rating.

Teacher adherence ratings will be designed and tested during the pilot.

Child quiz data will be collected during the pilot. Stigma and appraisal components have been standardised (Underwood et al., in press): we will check current data follows the same pattern, and validate the remaining components of the quiz against the other study measures (M&MF, CORS, see 12.3).

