12.3 Proposed primary and secondary questionnaire outcome measures

- We plan to use the following instrument as the potential primary outcome for the future RCT, Me and My Feelings (Deighton et al., 2013). This comprises 16 items, each rated 0 (best) to 2 (worst), measuring emotional (M&MF-E) and behavioral (M&MF-B) difficulties (M&MF-E, ten items; borderline/clinical cut-off >9; M&MF-B, six items; borderline/clinical cut-off >5). The measure is designed specifically for use in schools to evaluate public health initiatives, and has been widely used with children of this age group.

Proposed secondary outcomes for the future RCT are:

- The Children's Outcome Rating Scale (CORS, Duncan, Miller & Sparks, 2003) measures wellbeing/distress across four items, each rated 0 (worst) to 10 (best); clinical cut-off <32. The measure is widely used with children of this age.
- Children complete a quiz assessing learning from CUES-Ed (see Appendix 1). The quiz has been completed by large numbers of children during in-service delivery of CUES-Ed, so is acceptable for completion, with face validity. We are in the process of establishing norms, and will validate the measure as part of this pilot study.
- Teachers complete a rating of whole class behaviour involving estimates of the proportion of the class displaying particular behaviours 'always' or 'never', with the remainder displaying the behaviour 'sometimes'. We will validate this measure as part of this pilot study (see Appendix 2).

In addition:

- *Teacher adherence* data will be collected from a checklist to be standardised during the study.

- *Child attendance* data will be collected from the class register

13. Participant timeline

The delivery timeline needs to fit school terms, so has been designed to accommodate breaks.

Week	Study phase	Activity
-6+	Pre-engagement	
 • Approach local authority
-4+	Engagement	
 • Approach headteachers. • As part of consent, heads check teacher availability. • Headteacher consent • Teacher consent
-3 to -2	Participation, pre-randomisation	
 • Letter, information sheet and consent sent to parents • Classes informed of study by teacher using video from research team
-1 to 0	Baseline	
 • Child assent • Child measures • Teacher measures
0	Randomisation	
 • Research team informs school of allocation

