18.1 Data collection methods

Outcome measures (child emotional/behavioural problems, child wellbeing, teacher rated class behaviour) will be completed by children and teachers at 0, 8 and 16-weeks, on paper, with support from the research worker as required. Measures will be completed as a group in the classroom. Assessments should occur within a 1-month window of their calendar date, counted from the day of randomisation. Assessments will be collected by teachers, checking child assent and cross-referencing with parental consent. Assessment packs for children with both parental consent and child assent will be stored in the classroom, securely, separately from those without consent/assent. Once the final assessments are completed, the research team will collect the secured data and confidentially destroy, without access, data for children without consent/assent for research use. Data for children with both parental consent and child assent will be returned to the research team's trust base for entry.

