20.2 Secondary outcome analysis

The potential primary outcome the M&MF will be summarised using a mixed effects linear regression, fitting a random effect to explain the heterogeneity across school and class. Fixed effects will include baseline score, child sex and age. The between-group summary effect will be reported with the 95% confidence interval and intra-cluster correlation.

All other secondary outcome measures will be summarised descriptively and to show levels of completeness.

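### M&MF and CORS, the only comparators named for the child quiz's remaining components, are not sufficient to show that the quiz measures learning; a comparison by arm should be added

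*Protocol*

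**What the plan says.** Validating the child quiz is a secondary objective (Protocol synopsis and section 7.3), and the quiz is a proposed secondary outcome of the future trial. Section 12.3 gives its purpose: "Children complete a quiz assessing learning from CUES-Ed". The evidence claimed for it so far is acceptability and face validity.

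Section 12.2 divides the quiz in two. For one part, "Stigma and appraisal components have been standardised", and the pilot will check that its data follow the same pattern. For the rest, the plan is to "validate the remaining components of the quiz against the other study measures (M&MF, CORS, see 12.3"). Section 12.3 describes M&MF as "measuring emotional (M&MF-E) and behavioral (M&MF-B) difficulties" and says that CORS "measures wellbeing/distress across four items, each rated 0 (worst) to 10 (best); clinical cut-off <32".

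On analysis, section 20.2 plans a mixed model with a between-group effect for M&MF and then states: "All other secondary outcome measures will be summarised descriptively and to show levels of completeness". Section 20.4 adds psychometric analyses to validate the quiz, without saying which.

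**The concern.** The comparators named for the remaining components belong to a different construct from the one the quiz is said to measure. A child without symptoms may know all of the programme content or none of it, and so may a child with symptoms. A weak correlation with M&MF or CORS is therefore compatible with a good learning measure. A strong one could come from mood, general wellbeing or response style. At baseline no participating class has yet been taught the programme in the trial, so a correlation there says little about learning from it.

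What is at stake is whether the full trial keeps or drops this secondary outcome on evidence that bears on what the quiz is meant to measure. The design already supplies more direct evidence, namely quiz scores from taught and untaught classes, but the protocol does not say that it will be used for this purpose.

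**Working it through.** The protocol gives no figure for quiz validation, so there is nothing to reproduce. The point is checked by setting the sections side by side, followed by two illustrations on stated assumptions.

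**Sections compared**
- Construct: learning from CUES-Ed (12.3).
- Comparators for the remaining components: M&MF and CORS only (12.2), which measure difficulties and wellbeing/distress (12.3).
- A contrast within 12.2 itself: the teacher rating of class behaviour is to be compared with an observer's rating, which is a second measure of the same thing. The quiz has no counterpart of that kind.
- Data available: the quiz is marked at 0, 8 and 16 weeks in the 8.2 flowchart. Schools are randomised 1:1 (8.1). Waitlist classes complete the 8- and 16-week measures untaught (section 13).
- Analyses named: a between-group estimate for M&MF only (20.2), and unspecified psychometric analyses for the quiz (20.4). No quiz comparison by arm, exposure or attendance is named.
- Collection: section 18.1 lists the measures as "Outcome measures (child emotional/behavioural problems, child wellbeing, teacher rated class behaviour) will be completed by children and teachers". The quiz is not in that list, although the 8.2 flowchart schedules it.

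**Illustration (a): how much correlation teaching alone would create**

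Assume that CUES-Ed raises quiz scores by dQ and changes M&MF by dM (absolute size, in within-arm SDs), with equal arms and no within-arm association. The pooled correlation is then, in absolute size,

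r = (dQ/2 × dM/2) / √[(1 + dQ²/4)(1 + dM²/4)].

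- dQ = 0.5, dM = 0.3: r = 0.036
- dQ = 0.8, dM = 0.3: r = 0.055
- dQ = 1.0, dM = 0.3: r = (0.5 × 0.15) / √(1.25 × 1.0225) = 0.066
- dM = 0: r = 0 for any dQ

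With 288 children (80% of 360, section 7.1.4), the approximate 95% half-width for a correlation near zero is 1.96/√285 = 0.116, before any allowance for clustering. A quiz that responded strongly to teaching could therefore show no discernible correlation with M&MF through teaching. This is only the part of a correlation that comes through exposure. Within-arm association could add to it or offset it, and would not by itself demonstrate learning.

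**Illustration (b): precision of a quiz contrast between arms**

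Take 288 children in 10 schools, which gives 144 per arm and 28.8 per school. In SD units, SE = √(2/144 × DE) with DE = 1 + (28.8 − 1) × ICC, and t on 8 df = 2.306. The ICCs are assumptions.

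| ICC | DE | SE | 95% half-width |
|---|---|---|---|
| 0.01 | 1.28 | 0.133 | ±0.31 SD |
| 0.05 | 2.39 | 0.182 | ±0.42 SD |
| 0.10 | 3.78 | 0.229 | ±0.53 SD |
| 0.15 | 5.17 | 0.268 | ±0.62 SD |

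Baseline adjustment would tend to narrow these intervals. Unequal school sizes and separate class-level clustering, both ignored here, would tend to widen them.

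**The case against.** The strongest reply has four parts.

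- **The analysis is not closed.** Section 20.2 concerns the reporting of outcomes, while validation falls under 20.4, whose psychometric analyses could include a known-groups or sensitivity-to-change analysis. Descriptive summaries might also be shown by arm, and an analysis plan is to follow before database lock. This stands. A reader might infer that the protocol rules out the randomised contrast, but it only fails to name it.
- **The items are not visible.** The quiz itself is not in the text available for review, and it is evidently not a pure knowledge test, since it has stigma and appraisal components. If some remaining components concern coping or self-care, association with wellbeing is ordinary convergent evidence. This also stands. A reader might infer that the M&MF and CORS comparison can tell us nothing whatever its result. The documents do not support that; they support only that it is insufficient for learning components.
- **A pooled correlation has several sources.** It would be tempting to say that a correlation after randomisation can arise only because the programme moves both scores. That is wrong, because within-arm association through mood, ability or response style also contributes. The correction does not rescue the comparators, since such a correlation would not show learning either.
- **An arm difference mixes the instrument with the programme.** A sound quiz would show no difference if delivery was poor, and teacher adherence is itself under test (sections 11.3 and 12.1). This is a good reason not to make the contrast the sole criterion. It is no reason to leave it out.

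What survives is that 12.2 does name comparators, and they address a different construct from the one in 12.3.

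**Conclusion.** The point holds in a limited form. For any quiz components meant to measure learning, agreement with M&MF and CORS is secondary evidence and not sufficient validation. More direct evidence, from data already scheduled in both arms, is not named in the protocol. This rests on the wording of 12.2 and 12.3 and on the schedule. It does not depend on the assumed effect sizes or ICCs, which only illustrate how weak the link through teaching could be (about 0 to 0.07) and how wide the contrast would be (about ±0.3 to ±0.6 SD).

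The point does not extend to the stigma and appraisal components. The omission from 18.1 is a minor inconsistency and carries none of the validity argument.

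Priority is low to moderate. Quiz validation is one of several secondary objectives, enters no progression criterion, and does not feed the sample-size parameters, which section 12.2 bases on M&MF. Provided the scheduled quiz data are collected, the analysis can still be added.

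**What to change.** - In 12.2 and 20.4, add sensitivity to teaching as validity evidence for the learning components, alongside the planned psychometric analyses and not as a sole pass/fail criterion.
- Report the CUES-Ed versus waitlist difference in quiz score at 8 and 16 weeks, adjusted for baseline quiz score and allowing for school and class clustering, as an estimate with its 95% CI.
- Interpret it together with teacher adherence, since a null result could reflect poor delivery as well as an insensitive quiz.
- State which quiz components are meant to measure learning. Report their correlations with M&MF and CORS within arm, as secondary evidence.
- Add the quiz to the list in 18.1 so that it matches the 8.2 flowchart.

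The cost is a few lines of wording and a small amount of extra modelling on data already scheduled. The drawback is imprecision: with ten schools, an interval that includes zero should not be read as showing that the quiz is invalid.
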